#### Study Drug Accountability Compliance

Study drug accountability compliance is tabulated for the full analysis set as the number and percentage of subjects in the following categories:

- $\geq 1$  kit dispensed
- Did not return  $\geq 1$  kit dispensed and discontinued the study
- Did not return any kit dispensed and discontinued the study

Kit dispensed and kit returned are identified from “yes” responses to the questions “was this kit dispensed” and “was this kit returned”, respectively. Subjects who have non-missing study drug last date are considered to have discontinued the study.

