8.1 SERIOUS ADVERSE EVENT

8.1.1 Definition of Serious Adverse Event (SAE)

An SAE is any event that meets any of the following criteria at any dose:

- Death
- Life-threatening
- Inpatient hospitalization or prolongation of existing hospitalization
- Persistent or significant disability/incapacity
- Congenital anomaly/birth defect in the offspring of a subject who received study drug
- Other: Important medical events that may not result in death, be life-threatening, or require hospitalization, may be considered an SAE when, based upon appropriate medical judgment, they may jeopardize the subject and may require medical or surgical intervention to prevent one of the outcomes listed in this definition. Examples of such events are (but not limited to):
 - o Intensive treatment in an emergency room or at home for allergic bronchospasm

- o Blood dyscrasias or convulsions that do not result in inpatient hospitalization
- o Development of drug dependency or drug abuse
- o Potential drug induced liver injury (see Section 8.1.6)
- Abuse or Overdose of medication
 - Potential study drug abuse (including cases of excessive non-compliance with study drug dosing instructions or subjects who discontinue treatment without returning study drug) should be documented in the source record and reported as an AE or SAE as appropriate. Investigators must monitor subjects for possible cases of abuse of study drug (subjects taking study drug for non-therapeutic purposes, e.g. for psychoactive effects such as high or euphoria). Investigators should obtain more information and explanation from subjects when there are study drug accountability discrepancies
 - Potential study drug overdose is defined in Section 8.1.4.

Definition of Terms (the below applies to both non-serious adverse events and serious adverse events).

Mild: Is usually transient and may require only minimal treatment or therapeutic intervention. The event does not generally interfere with usual activities of daily living.

Moderate: Is usually alleviated with additional specific therapeutic intervention. The event interferes with usual activities of daily living, causing discomfort but poses no significant or permanent risk of harm to the subject.

Severe: Interrupts usual activities of daily living, significantly affects clinical status, or may require intensive therapeutic intervention.

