## 4 ANALYSIS SETS, TREATMENT GROUPS, AND SUBGROUPS

### 4.1 Analysis Sets

The following analysis sets are evaluated and used for presentation and analysis of the data:

- Enrolled: Subjects who sign an informed consent form and are assigned a subject identification number, i.e., non-missing informed consent date. This analysis set is used mainly to assess study population and in by-subject listings.
- LTT participated: Subjects in the enrolled analysis set who participated in the LTT phase, i.e., non-missing IWRS baseline visit date. This analysis set is used mainly to assess study population.
- Safety: Subjects in the enrolled analysis set who take study drug, i.e., non-missing study drug start date/time. This analysis set is used to assess study population, exposure, and on-treatment safety, migraine days per month, and outcomes research.
  - Migraine: Subjects in the safety analysis set with  $\geq 14$  days of data (not necessarily consecutive) in both the OP analysis period and  $\geq 1$  month in the LTT analysis period. This analysis set is used to assess migraine days per month.
  - Follow-up: Subjects in the safety analysis set whose last contact date is in the follow-up safety analysis period. This analysis set is used to assess follow-up safety.
- Full: Subjects in the LTT participated or safety analysis set.
- Coronavirus Disease 2019 (COVID-19) impacted: Subjects in the enrolled analysis set who are impacted by COVID-19 (see Section 9.1.2).

See Section 7.1 for derived dates and Section 7.2 for analysis periods.

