## **7 CONVENTIONS**

### **7.1 Derived Dates**

Derived dates for defining analysis periods are defined as follows:

- Study drug date/time: Complete finding date/time corresponding to “yes” response to question about taking study medication and number of sprays  $> 0$  in the eDiary evening report or medication reconciliation form.
- Study drug start date/time: Earliest study drug date/time.
- Study drug end date/time: Latest study drug date/time.
- Study drug last date/time: Study drug end date/time derived only for subjects with non-missing response to the question “Did the subject complete the study?” on the Study Exit Status CRF. Thus, in an interim analysis, all post-baseline data are included for a subject who is still on study. At the last database lock, the study drug last date is equal to the study drug end date.
- LTT start date/time: Earlier of (1) study drug start date/time, and (2) IWRS baseline visit date (i.e., Baseline/Day 1 visit date from the BHV3500\_202 IWRS Visit Report csv file).
- LTT end date/time: Later of (1) latest complete finding date/time in the eDiary on or after the LTT start date/time, and (2) latest complete visit date on or after the LTT start date through the Week 52/Early Termination visit date, and excluding the Follow-up Week 2 visit date, from the Visit Date CRFs.

- LTT last date/time: LTT end date/time derived only for subjects with non-missing response to the question “Did the subject complete the study?” on the Study Exit Status CRF. Thus, in an interim analysis, all LTT data are included for a subject who is still on study. At the last database lock, the LTT last date is equal to the LTT end date.
- OP start date/time: Earliest complete finding date/time in the eDiary before the LTT start date/time.
- OP end date/time: Latest complete finding date/time in the eDiary before the LTT start date/time.
- COVID-19 visit date: (1) Complete visit date, if it exists; (2) otherwise, complete date the visit was planned to occur for a missed visit (see Section 9.1.1).

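### The unreturned-kit rows in SAP 6.2.6.2 cannot count subjects who were dispensed drug, have no recorded dose and left the study without returning their kits

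*SAP*

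**What the plan says.** The table under Study Drug Accountability Compliance (SAP 6.2.6.2) is introduced as follows: "Study drug accountability compliance is tabulated for the full analysis set as the number and percentage of subjects in the following categories". It has three rows: at least one kit dispensed; at least one dispensed kit not returned, and left the study; no dispensed kit returned, and left the study. The section gives one rule for having left: "Subjects who have non-missing study drug last date are considered to have discontinued the study".

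The terms used are defined elsewhere in the SAP:

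- Section 4.1 defines the population: "Full: Subjects in the LTT participated or safety analysis set". The LTT participated set is "Subjects in the enrolled analysis set who participated in the LTT phase, i.e., non-missing IWRS baseline visit date". No dose is needed to belong to it.
- Section 7.1 defines study drug last date: "Study drug end date/time derived only for subjects with non-missing response to the question" about study completion on the Study Exit Status CRF.
- Section 7.1 also gives "Study drug end date/time: Latest study drug date/time", and a study drug date needs a yes "response to question about taking study medication and number of sprays" above zero, in the evening report or the medication reconciliation form. None of these derived dates is imputed.

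Protocol 7.4 and 8.1.1 give unreturned drug some weight. They place "subjects who discontinue treatment without returning study drug" among the cases of potential abuse to be documented in the source record and reported as an AE or SAE as appropriate.

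**The concern.** Every subject with a recorded dose is already in the safety set. Choosing the full analysis set therefore adds only LTT participants with no recorded dose, and the exit rule bars exactly those subjects from both unreturned-kit rows. They enter the population and the dispensed row but can never enter a non-return count.

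The plan foresees this group. Drug is handed out at the baseline visit (Protocol 4.3.3), subjects who have treated no migraine by Week 8 are discontinued (Protocol 4.1 and 6.6), and SAP 6.2.3.2 has a disposition category for LTT participants who were not treated. SAP 6.2.6 also treats a day without eDiary dosing data as a day without drug, so a subject who used the drug but never reported it falls into the same group.

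At stake is whether the one accountability table that includes undosed subjects reports unreturned kits correctly. The other accountability tables in 6.2.6.1 (accountability exposure, and eDiary versus accountability) are restricted to the safety set.

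**Working it through.** No figure in the plan depends on this rule, so there is none to reproduce. The check is to apply the definitions case by case.

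**Step 1: when each date exists.**

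- Study drug last date = a dose recorded in either source AND an exit response.
- LTT last date = LTT end date AND an exit response (SAP 7.1). LTT end date is the later of the latest eDiary finding and the latest LTT visit date on or after LTT start. An LTT participant without a dose has it through the recorded baseline visit. A dosed subject has it through the dose record itself.

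**Step 2: apply both rules.** Take a subject in the full set with 2 kits dispensed; 1 = counted, 0 = not counted. The two figures in each of the last two columns are for the row of at least one kit unreturned and the row of no kit returned.

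| Dose recorded | Exit response | Kits returned | Dispensed row | SAP rule | LTT last date |
|---|---|---|---|---|---|
| no | yes | 0 | 1 | 0, 0 | 1, 1 |
| no | yes | 1 | 1 | 0, 0 | 1, 0 |
| no | yes | 2 | 1 | 0, 0 | 0, 0 |
| yes | yes | 0 | 1 | 1, 1 | 1, 1 |
| yes | yes | 1 | 1 | 1, 0 | 1, 0 |
| yes | yes | 2 | 1 | 0, 0 | 0, 0 |
| either | no (ongoing at an interim lock) | 0, 1 or 2 | 1 | 0, 0 | 0, 0 |

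The two rules differ only in the first two lines: undosed subjects who have left with a kit unreturned. Using the exit response directly gives the same results as LTT last date in every line.

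**Step 3: possible size.** The documents give neither the number of undosed LTT participants nor their return rate, so all inputs here are assumed except the planned 600 treated subjects. Let t be the treated non-returners, U the undosed subjects with kits dispensed, and s the share of U not returning. The denominator is taken as the full set; the counting rules for frequency tables are in the Core SAP, which is not available here.

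- SAP rule: t / (600 + U)
- Revised rule: (t + s × U) / (600 + U)

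| U | t | SAP rule | Revised, s = 25% | Revised, s = 100% |
|---|---|---|---|---|
| 6 | 6 | 0.99% | 1.24% | 1.98% |
| 6 | 30 | 4.95% | 5.20% | 5.94% |
| 30 | 6 | 0.95% | 2.14% | 5.71% |
| 30 | 30 | 4.76% | 5.95% | 9.52% |
| 60 | 6 | 0.91% | 3.18% | 10.00% |
| 60 | 30 | 4.55% | 6.82% | 13.64% |

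For example, with U = 30 and t = 6, the SAP rule gives 6/630 = 0.95%, and the revised rule with s = 25% gives (6 + 7.5)/630 = 2.14%. The shortfall is s × U / (600 + U). It runs from 1.5/606 = 0.25 percentage points to 60/660 = 9.09 points over this grid, and is zero if there are no such subjects.

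**The case against.** The strongest reply is that nothing is lost from the study record and little depends on this table. Most of that stands.

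- **Visibility.** The by-subject accountability listing in SAP 6.2.6.1 runs on the same full set and shows dispensed and returned status for each kit. SAP 6.2.3.2 counts the untreated LTT participants. What is missing is a tabulated count.
- **Abuse.** A reader might infer that potential abuse cases are being hidden. The documents do not support that. The abuse endpoint is built on AE reports, not on kit returns. For a subject with no study drug start date, SAP 7.2 treats all measurements as pre-treatment, and the pre-treatment AE overview for the enrolled set (6.4.1.2) has a row for potential drug abuse. A reported event would therefore appear there, provided the site reports it. The SAP presents the kit table as a compliance measure.
- **Completers.** A reader might also infer that the table is wrong because dosed completers have a study drug last date and so meet the condition too. This is a matter of labelling. The rule's practical effect is to leave out subjects still on study at an interim lock. A completer counts only if a kit is unreturned, and Protocol 4.3.5 requires all drug to be returned. LTT last date would include completers as well.
- **Rarity.** Entrants must have 2 to 8 moderate or severe attacks per month and must have treated at least 2 in the observation phase (Protocol 5.2), so having no recorded dose at all should be uncommon. That is plausible, but the Week 8 discontinuation rule shows that the case is expected.

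None of this changes the mechanical result: as written, the rule returns zero for this group whatever the subjects did with their kits.

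**Conclusion.** The point holds, in a narrow form. Both unreturned-kit rows exclude every LTT participant who has no dose in the evening report or the reconciliation form, even after a completed study exit, while the same subjects count in the dispensed row. The non-return count is understated if at least one such subject left with a kit unreturned, and is correct otherwise. The exclusion follows from the definitions alone. Its size does not: the percentages shown rest on assumed numbers of undosed subjects and assumed return rates, and should not be read as an estimate.

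No primary endpoint, AE rate, laboratory result or exposure total is affected. Severity: minor.

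**What to change.** In SAP 6.2.6.2, replace the condition of a non-missing study drug last date with a non-missing LTT last date, which 7.1 already derives. A non-missing Study Exit Status completion response would also serve; SAP 6.2.6.1 already uses it to define discontinuation in the Kaplan-Meier tables of time on drug and time in LTT. Either choice still leaves out subjects who are ongoing at an interim lock, and neither changes the rows for dosed subjects in the cases checked.

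Optionally, relabel the condition as no longer in the study, because it includes completers.

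The cost is one line of SAP text and one variable in the table program. No new data are needed.

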### 6.2.6.3 *Concomitant Medications*

The following concomitant non-study medications are tabulated by therapeutic class and preferred name for the safety analysis set: all; migraine standard of care; prophylactic migraine.

In addition, current or concomitant calcitonin gene-related peptide (CGRP) receptor antagonist biologics are tabulated analogously to support safety subgroup analyses and align with subgroups specified in Section 4.3. Refer to the Zavegeptan Core SAP for preferred names.

The following non-study medications taken on or after LTT start are tabulated by therapeutic class and preferred name for the safety analysis set: all; migraine standard of care; prophylactic migraine. These are medications with LTT start date  $\leq$  imputed start date or imputed stop date.

Medications are displayed in descending order of overall frequency within therapeutic class and preferred name. Imputed medication start and stop dates are used to assign non-study medication type (previous, current, concomitant, or follow-up) to all non-study medications except rescue

medications. Refer to the Zavegeptan Core SAP for definitions of non-study medication types, non-study medication counting rules in frequency tables, and non-study medication start and stop date imputation.

A by-subject listing of non-study medications is provided by therapeutic class and preferred name for the enrolled analysis set. Acute migraine and prophylactic migraine medications are identified, as well as medication type. The listing also displays treatment days derived from the imputed start date, and COVID-19 visit impact code for visits impacted by COVID-19 (see Section 9.1.5.2). Refer to the Zavegeptan Core SAP for additional listing contents.

The following conventions apply to non-study medications:

- Non-study medications are identified from those reported on the Concomitant Medication CRF, which links medical history and AE terms respectively to the Medical History and AE CRFs using numeric variables.
- Migraine standard of care medications are defined as either acute migraine or prophylactic migraine medications from the indication panel of the CRF.

### **6.3 Efficacy**

Not applicable.

### **6.4 Safety**

Safety analyses are based on the safety analysis set, unless otherwise noted. Safety parameters include the following: deaths; AEs; laboratory tests; vital signs; physical measurements; electrocardiograms (ECGs); and S-STS.

Refer to the Zavegeptan Core SAP for slotting safety parameters into analysis periods.

Select safety parameters are tabulated descriptively as continuous variables at baseline and each scheduled visit over time during the on-treatment and follow-up safety analysis periods.

Measurements are slotted into analysis periods and analysis visits using the following steps:

- 1) Measurements are slotted into the pre-LTT, LTT and follow-up analysis periods.
- 2) Measurements are slotted into analysis visits in the analysis periods listed in the previous step.
- 3) Measurements are slotted into safety analysis periods (pre-treatment, on-treatment and follow-up).

For tables of safety parameters excluding laboratory tests summarized over time, if a subject has multiple values in an analysis visit window in a safety analysis period, then the non-missing value measured closest to the target date for the visit is used. In the case of a tie, the last non-missing value measured is used. In these tables, results are also summarized at the EOT visit using the last non-missing value measured in the on-treatment safety analysis period. See Sections 6.4.3.1 and 6.4.4.1 for further handling of ties on the same measurement date or time.

Note that a different algorithm is used for selecting a laboratory test value in an analysis visit window (see Section 6.4.2.3).

See Sections 6.2.4, 7.2, and 7.3 for definitions of baseline, analysis periods, and analysis visit windows, respectively.

By-subject listings of safety parameters are described in subsections. In addition, a by-subject listing of procedures is provided for the enrolled analysis set. Listings identify events or findings during the on-treatment safety analysis period, and display COVID-19 visit impact code for visits impacted by COVID-19 (see Section 9.1.5.2).

The terms “on-treatment” and “follow-up” apply to the on-treatment and follow-up safety analysis periods, respectively.

#### **6.4.1 Adverse Events**

Refer to the Zavegeptan Core SAP for AE start date imputation, AE counting rules, definition of treatment-emergent adverse events (TEAEs), definition of AEs related to study drug, definition of AEs of special interest, definition of exposure-adjusted multiple occurrences of unique AEs, and AE listing contents.

Tables present the number and percentage of subjects experiencing AEs by SOC and PT, unless specified otherwise.

The following by-subject AE listings are provided for the enrolled analysis set, unless specified otherwise: AEs (displays COVID-19 visit impact code for visits impacted by COVID-19; see Section 9.1.5.2); SAEs; AEs leading to study drug discontinuation for the safety analysis set; and AEs of special interest (i.e., potential drug abuse, medication-overuse headache, hepatic-related, cardiovascular, suicidality, and local irritation). TEAEs are identified.

##### **6.4.1.1 Deaths**

Deaths are identified from any the following sources:

- AE CRF: PT or reported term containing “death”, outcome of fatal, “yes” response to the question “Did the AE result in death?”, or non-missing death date.
- Study Exit Status CRF: study non-completion reason of death.

Deaths are tabulated by analysis period for the enrolled analysis set.

A by-subject listing of deaths is provided for the enrolled analysis set, and displays all CRF sources of death, safety analysis period, death date (see Section 7.1), study day derived from the death date, treatment day derived from the death date, and the following AE parameters: non-imputed start date; end date; SOC; PT; verbatim term; outcome; and response to the question “Did the AE result in death?”. Refer to the Zavegeptan Core SAP for additional details.

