- Last contact date: (1) Earliest complete death date from the AE CRF, if it exists; (2) otherwise, the maximum complete date of the following: AE start or stop; COVID-19 visit only for in-person or remote visits; ECG; eDiary finding; informed consent; IWRS baseline visit; laboratory test collection; nasal inspection; non-study medication start or stop; physical exam; physical measurement; procedure; rating scale; questionnaire; vital sign; visit. If the last contact date is after the most recent raw database creation date, then it is set to the most recent raw database creation date.
- Death date: Last contact date derived only for subjects who died (see Section 6.4.1).

No imputations are performed on these derived dates. Complete dates are those with valid, non-missing day, month, and year.

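### SAP 6.4.1.1 counts a subject as dead when an AE term merely contains the word 'death', even if every field about that subject says otherwise

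*SAP*

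**What the plan says.** SAP 6.4.1.1 opens its rule with "Deaths are identified from any the following sources", so the sources are alternatives and one suffices. They are:

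- on the AE form, a text match or a fatal outcome: "AE CRF: PT or reported term containing “death”, outcome of fatal";
- also on the AE form, a 'yes' "response to the question “Did the AE result in death?”, or non-missing death date";
- on the exit form: "Study Exit Status CRF: study non-completion reason of death".

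The output follows in the same section: "Deaths are tabulated by analysis period for the enrolled analysis set". A by-subject listing shows the sources that flagged each death, with the preferred and verbatim terms, the outcome and the answer on whether the AE led to death. SAP 6.4.7 puts deaths on the safety-narrative list. The AE overview in SAP 6.4.1.2 has no row for deaths, so it gives no separate count.

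SAP 7.1 dates the event: "Death date: Last contact date derived only for subjects who died". Last contact is itself defined in two steps: "Last contact date: (1) Earliest complete death date from the AE CRF, if it exists; (2) otherwise, the maximum complete date of the following", and that list covers visits, laboratory tests, eDiary entries, medications and similar records.

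SAP 6.4.1.1 sends the reader to the Zavegepant Core SAP for further details. That document is not available here.

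**The concern.** A word search on an AE term does not establish who died, or that anyone did. The investigator's reported term is free text, and the rule searches it without requiring that the death be the subject's own. Protocol 8 takes AEs from spontaneous report and open-ended questioning, and Protocol 8.3.1 collects non-serious AEs from screening to the follow-up safety visit.

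Two kinds of wording could trigger the match. The first is a symptom described by its cause, such as poor sleep after a death in the family. The second comes from suicidality monitoring. The S-STS is completed at least monthly, and Protocol 6.3.5 requires an AE or SAE record when the investigator judges a subject to be at risk. A term such as 'thoughts of death' would then classify a living subject as dead.

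What is at stake is the count for the gravest safety outcome, in a study whose only primary objective is safety and tolerability. If no subject dies, a single false match makes the difference between none and one. SAP 8 applies the same tables to the interim report that supports the new drug application, so a subject still taking part could be listed there with a date of death.

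**Working it through.** **Inputs.** The flagging rule and table population are from SAP 6.4.1.1, and the dates from SAP 7.1. About 800 screened and 600 treated are from SAP 2.1. The upper bound of 0.005 for zero events in 600 is from SAP 5.

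**1. The plan's own figure.** The exact one-sided 95% upper bound for 0 of 600 is 1 − 0.05^(1/600) = 0.00498, and the rule of three gives 3/600 = 0.0050. The stated 0.005 is reproduced. The point below does not depend on it.

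**2. The rule as logic.** Dead = (term contains 'death') OR (fatal outcome) OR (AE led to death = yes) OR (death date present) OR (exit reason = death). The confirmed rule drops the first condition as sufficient on its own. In the first seven rows below, which are hypothetical terms, the outcome is recovered, the answer on resulting death is no, and there is no death date or exit reason of death.

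| AE term | Contains 'death' | Rule as written | Confirmed rule |
|---|---|---|---|
| insomnia due to death in family | yes | dead | not dead |
| thoughts of death | yes | dead | not dead |
| grief after death of parent | yes | dead | not dead |
| fear of death | yes | dead | not dead |
| fetal death | yes | dead | not dead |
| bereavement | no | not dead | not dead |
| miscarriage | no | not dead | not dead |
| death (a true death, structured fields still blank) | yes | dead | unconfirmed, queried |

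The last row matters for the choice of fix. If the text match were simply deleted, that subject would not be found at all.

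**3. The date.** A text-only match has no death date on the AE form, so the second step of the last contact definition applies. The derived death date is the subject's latest complete record of any listed kind, which may be a diary entry or a visit.

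**4. Size.** Deaths are tabulated for the enrolled set, taken as about 800. With no true deaths and one false match, the count goes from 0/800 = 0% to 1/800 = 0.125%, or about 0.13%. Two false matches give 2/800 = 0.25%. The number of false matches is an assumption, because the documents give no rate for such terms.

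**5. Reach.** SAP 7.1 derives the death date from the last contact date, not the reverse, so a false flag does not move last contact or any analysis period in SAP 7.2. The primary endpoint components in SAP Table 1 are AEs in at least 5% of treated subjects by intensity, SAEs, AEs leading to discontinuation, and grade 3 to 4 laboratory abnormalities. None of them uses the death flag.

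**The case against.** The strongest defence is that the match is a deliberate safety net. Deaths should be sought with high sensitivity, and structured fields can lag. SAP 1.2 and SAP 8 allow an interim report from a lock before the last subject's last visit, and SAP 6.2.3.3 treats a blank completion response before final lock as ongoing. At that point a term of 'death' might be the only signal. This stands as a reason to keep the match for finding cases. It is not a reason to count them unconfirmed.

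The second defence is visibility. The listing shows the source, the verbatim term, the outcome and the answer on resulting death, and every flagged subject is named for a narrative. With few deaths expected, a false match should be noticed. That also stands, but no stated rule takes the subject out of the table, so a correction after lock would depart from the SAP.

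Third, the Core SAP may add a restriction. That cannot be checked. SAP 6.4.1.1 states the identification rule itself and leaves only additional details to the other document.

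Fourth, such wording may be rare. Protocol 8 asks for the diagnosis where one is identified, which discourages narrative terms. This limits how often the problem would arise but does not remove it.

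**Conclusion.** The point holds as a gap in the stated rule. A living subject with 'death' anywhere in an AE term would be tabulated as dead and given a death date, and nothing in the two documents removes the case. Its size is 0 to 1 of about 800 (0.13%) per false match. This assumes no true deaths, one such term and no restriction in the Core SAP.

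Three stronger readings are not supported:

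- A reader might infer that any bereavement or pregnancy loss becomes a death. Only the literal string does so. The fetal route is remote: contraception and monthly pregnancy tests are required, and Protocol 8.1.5 sends pregnancy outcomes to a Pregnancy Report Form, which is not a source in SAP 6.4.1.1.
- A reader might set one false death against the sample-size statement, since the one-sided 95% upper bound for 1 of 600 is 0.79%, above the stated 5 per 1,000. But SAP 5 concerns AEs with zero events in treated subjects, while deaths are tabulated for the enrolled set and no confidence interval is planned for them.
- A reader might infer that the primary safety results are affected. No primary endpoint component or analysis period changes.

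**What to change.** In SAP 6.4.1.1, count a death only when at least one subject-specific field confirms it: a fatal outcome, a 'yes' on whether the AE led to death, a death date, or an exit reason of death.

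Keep the text match on the preferred and reported terms as a trigger for case finding. Each text-only match is queried with the site and resolved before any interim or final lock. Any match still open at the lock appears in the deaths listing marked as unconfirmed and is left out of the deaths table. The death date in SAP 7.1 then applies to confirmed deaths only.

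The cost is a short change to one section, one line of code and the query work. There is one small downside. A true death whose structured fields are all still blank at an interim lock would show as unconfirmed until resolved. It would remain visible in the listing, which would not be so if the text match were deleted.
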